Parents' experiences in family meetings and perspectives on communication with the clinical team will be measured with a pre-intervention survey or interview. Parents' acceptability of the parent preparation process for the family meeting and of the written summary received after the meeting will be measured during the post-intervention survey and interview.

TABLE 1: SCHEDULE OF STUDY PROCEDURES

Clinicians and Parents Participating in Co-design		
Study Phase	Enrollment	Co-design
Visit Number	1	2-12
Study Days	1	2-400
Enrollment	X	
Get Feedback through Focus Group		X
Measure Engagement through Survey		X

Clinicians Participating in Intervention				
Study Phase	Enrollment	Intervention	Follow-up	
Visit Number	1	2-11	5-30	6-21
Study Days	1	2-200	9-500	36-310
Enrollment	X			
Communication Skills Training (up to 10 hours)		X		
Online course evaluation survey including Maslach burnout score and COVID-19 questions		X		
Post-CST actual clinical encounters			X	
Follow-up actual meeting survey			X	
Acceptability interview				X

Clinicians Not Participating in Intervention		
Study Phase	Enrollment	Pre or Post-Intervention
Visit Number	1	2-17
Study Days	1	2-540
Enrollment	X	
Observed Family Meeting		X
Online Survey		X

Parent-patient Dyads Participating in the Survey (Prior to Intervention)		
Study Phase	Enrollment	Follow-Up
Visit Number	1	
Study Days	1	2-730
Enrollment	X	
Online Survey	X	
Medical record review (patient or family not contacted)		X

Parent-patient Dyads Participating in the Interview (Prior to Intervention)		
Study Phase	Enrollment	
Visit Number	1	
Study Days	1	
Enrollment	X	
In-person Interview	X	

Parent-patient Dyads Participating in the Survey and Interview (After Intervention)					
Study Phase	Enrollment	Follow-Up	Follow-Up	Follow-Up	Follow-Up
Visit Number	1	2	3	4	
Study Days	1	1-10	1-60	2-60	2-730
Enrollment	X				
Recording of Family Meeting		X			
Online Survey			X		
Interview				X	
Medical record review (patient or family not contacted)					X

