1.2 Name and Description of Investigational Product or Intervention

The communication skills training (CST) program for clinicians will encourage the use of best practices in conducting family meetings where teams give bad news and elicit goals of care as well as build team collaboration. The CST will be developed by modifying the VitalTalk³⁶ CST to adapt it to interprofessional training, the pediatric CICU setting, and CHOP-developed Family Meeting Resources. The family-facing intervention includes standardized preparation for family meetings and provides a written summary of the family meeting to families. The combined aspects of the intervention are now known as CICU Teams and Loved ones Communicating (CICU TALC).

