After the consent process, clinicians will go through the interprofessional CST. The CST will occur over the course of 10 hours and will include short didactic sessions around giving bad news, eliciting parental goals, the core competencies of interprofessional collaborative practice⁸⁸, and adaptation for the CICU of the common components of a family meeting as represented in the CHOP Family Meeting Resources (http://intranet.chop.edu/sites/social_work/family-meeting-resources.html). Skills practice groups will include no more than 6 learners at a time. Didactic sessions may be in person or may be performed independently online as needed. Whether in-person or online, sessions may be audio or video recorded. There will be an online survey immediately after the CST to evaluate the clinicians' perception of effectiveness of the course. One month after the completion of the CST, a random sample of 8 participants will take part in a 15-30 minute acceptability interview regarding the CST.

Following the CST, a set of at least 23 actual family meeting encounters with trained clinicians will be audio recorded and coded.

A measure of team function will be assessed pre and post-CST by comparing the amount of time different members of the clinical team speak, and the kind of input offered by members of different disciplines within the team for simulated and actual family meetings. Team member perception and satisfaction with collaboration will be measured after their participation in clinical encounters both pre and post-CST by administering the modified Baggs CSACD-N tool to all clinician team members who participate in an actual encounter. This tool will capture each discipline's experience with collaboration with other team members and satisfaction with care decisions. Finally, fidelity of clinician behavior to the intended intervention in post-intervention family meetings will be determined by a fidelity checklist.

Actual meetings will each last 30-120 minutes. Clinicians participating in the intervention will be enrolled for the entirety of the study, lasting up to four years. They will have at least 21 points of contact with the research team, but some clinicians may participate more frequently due to the unknown composition of the observed actual family meetings.

Clinicians Not Participating in Intervention

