3.3 Study Duration, Enrollment and Number of Sites

3.3.1 Duration of Study Participation

Study duration for clinicians and parents participating in the co-design is expected to last up to 12 months since their schedules are not conducive to completing the tasks more efficiently. The expectation is that they will meet approximately one hour a month for 11 months.

Study duration for clinicians participating in the intervention is expected to last up to 4 years. The CST intervention will occur over the course of 10 hours lasting over several months. Clinicians will have at least 21 points of contact with the research team, but some clinicians may participate more frequently due to the unknown composition of the observed actual family meetings.

For each post-family meeting survey administration, clinicians will be contacted no more than 3 times via email to request that they complete the survey. Templates for the emails requesting that they complete the surveys are demonstrated in Appendix 11.6 and Appendix 11.7. The surveys are expected to take approximately 5-10 minutes to complete. The full survey is located in Appendix 11.10.

Study duration for non-participating clinicians will last the duration of their family meeting (30-90 minutes), and post-meeting surveys are expected to take approximately 5-10 minutes to complete.

Study duration for parent-patient dyads participating prior to the intervention will last approximately 20 minutes for those participating in the survey for visit 1 and their medical record review will occur at discharge from the hospital which may range from 2-730 days after enrollment. Study duration will be 30-60 minutes for those participating in the interview.

Study duration for parent-patient dyads participating after the intervention will last approximately 30-60 minutes for the recording of the family meeting for visit 2, 20 minutes

for those participating in the survey for visit 3, and approximately 20 minutes for those participating in the interview for visit 4. Medical record review will occur at discharge from the hospital which may range from 2-730 days after enrollment.

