3.3.2 Total Number of Study Sites/Total Number of Subjects Projected

The study will be conducted within the Children's Hospital of Philadelphia. The co-design phase will be conducted with participants from units within the hospital and parents with children who had previously been hospitalized at CHOP, and the intervention and evaluation of the intervention will occur exclusively in the CICU at CHOP.

For clinicians participating in the co-design, approximately 15 clinician staff will be enrolled and 5 parents will be enrolled.

For clinician subjects participating in the intervention, recruitment will stop when at least 20 CICU clinicians are enrolled.

For non-participating clinicians, recruitment will stop when we obtain at least 56 family meetings per discipline of participating clinician team member.

We estimate that approximately 300 clinicians who are not participating in the intervention may be observed subjects in the actual meetings.

For parent-patient dyads participating prior to the intervention, recruitment will stop when 100 evaluable parent-patient dyads are enrolled for the survey and 30 evaluable parent-patient dyads are enrolled for the interview.

For parent-patient dyads participating after the intervention, recruitment will stop when up to 30 evaluable parent-patient dyads are enrolled for the survey and a subset of up to 15 parent-patient dyads will be asked to participate in the interview.

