4.5 Follow-Up Phase

After clinicians who participate in the intervention are trained, their communication and team function skills will be assessed in actual encounters. Actual encounters with parents and patients will involve participating clinicians and non-participating clinicians.

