## Statistical Analysis Plan

Aim 2: Pilot test the co-design-adapted CICU TALC with CICU parents and clinicians to determine:

a) Acceptability of intervention: Hypothesis: Respondents will endorse above a critical threshold of acceptability on satisfaction instruments to 20 clinicians and 23 parents and in semi-structured interviews.

Analytic plan: A constructivist grounded theory approach will guide qualitative analysis of interview transcripts regarding acceptability of the intervention. Descriptive statistics will be calculated for quantitative data from the acceptability survey.

b) Feasibility of enrollment and data collection, and fidelity: Hypothesis: Feasibility will be defined by: i) 30% parental and 50% clinician enrollment and consent rates, and 80% subject retention, and attrition; ii) ability to collect outcomes data from 46 patients (CICU length of stay), from 46 parents and from 50% of eligible team members. and iii) intervention fidelity with 95% of enrolled parents and clinicians receiving parent-directed and team-directed interventions.

Analytic Plan: Data completeness and accuracy will be monitored. I will calculate descriptive summaries including means and standard deviations for continuous variables, and proportions for categorical variables. As appropriate for pilot trials, analyses will focus on estimating proportions of binary feasibility and fidelity endpoints and constructing 95% CIs. Analyses of parent-reported outcomes will primarily be descriptive. Means and standard deviations along with 95% confidence intervals will be calculated.

c) Impact of CICU TALC on CICU parent and team behavior in family meetings. Hypothesis: the intervention will increase parent speaking time by 60%, elicitation of parental concerns to 40%, and response to parental emotion by 30%. I will audio record 230 CICU family meetings occurring before CICU TALC is initiated and 230 after initiation and use quantitative methods to measure pre-vs-post differences in a) speaking time of parents and physicians; b) elicitation of parental concerns; and c) response to parental emotion.

Analytic Plan:

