- Speaking time will be analyzed by comparing the change in the number of words spoken by physicians versus parents speak in pre- and post-CICU TALC meetings using generalized linear regression with binomial link function controlling for the length of the meetings. Means and standard deviations will be calculated for the tool and t-tests will determine if significant differences exist for the two groups pre and post-CICU TALC.
- Elicitation of parental concerns and empathic response to parental emotion will be determined through quantitative coding. Each skill will be analyzed separately, using the cutoffs to identify skill proficiency as used by Back. Univariate relationship pre/post intervention by outcomes (Table 1)
  - If the outcomes (skills acquisition scores) are continuous and satisfies the normality assumptions, then t-tests will be appropriate to compare pre – intervention and post – intervention changes.

- If outcomes are continuous but not normally distributed, then a Wilcoxon Rank sum test will be appropriate to compare pre –intervention and post –intervention changes.
- If outcomes are binary (high vs low), then chi-square/fishers exact tests will be appropriate to compare pre –intervention and post –intervention changes.
- Similar statistical analysis will be performed to compare pre –intervention and post –intervention changes overall and for each type of participant.
- Analyses will be presented at the meeting-level as well as the participant-meeting level. Participant-meeting level data will be stratified by physician-type pending  $\geq 5$  participants in the pre- and post-intervention groups for each type.
- Relationship pre/post intervention by outcomes adjusted for participant and meeting level characteristics
  - If sample size allows and there are significant univariate associations, we will utilize mixed effect regression models to explore the relationship between the intervention and outcomes, first controlling for--gender and years of experience and accounting for correlation of repeated measurements within participants. If sample size allows, we will include other characteristics including number of participants at the meeting, proportion of speaking time by participant type, etc

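### The SAP's participant-level pre/post comparison takes no account of whether each clinician had completed training, and its cut-point (initiation of CICU TALC) does not match the protocol's post-training definition

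*SAP*

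**What the plan says.** **Cut-point.** SAP Aim 2c compares "family meetings occurring before CICU TALC is initiated and 230 after initiation". It gives no date for initiation, no rule tied to completing training, and no handling of meetings held while training is under way.

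Protocol 3.1 describes the post phase differently: "Following the CST, a set of at least 23 actual family meeting encounters with trained clinicians will be audio recorded and coded". Sections 3.1.5 and 4.5 also place these meetings after training.

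**Duration of training.** Protocol 3.3.1: "The CST intervention will occur over the course of 10 hours lasting over several months". For intervention clinicians, Table 1 gives CST at visits 2-11, days 2-200, and post-CST meetings at visits 5-30, days 9-500.

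**Who is in the post-phase recordings.** Protocol 4.5: "Actual encounters with parents and patients will involve participating clinicians and non-participating clinicians". Section 3.1.5 has the meetings of untrained clinicians recorded and coded, and 4.5.3 repeats the recording. At least 20 clinicians are to be trained, while "approximately 300 clinicians who are not participating in the intervention may be observed subjects in the actual meetings" (3.3.2).

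**Analysis.** SAP: "Analyses will be presented at the meeting-level as well as the participant-meeting level". Participant-meeting rows are compared pre versus post, overall and by participant type, and stratified by physician type. The optional mixed model first adjusts for gender and years of experience. Protocol 6.3.2 uses clinician fixed effects. Training status appears in none of these.

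**The concern.** Protocol section 2 states the purpose as finding out whether CST changes clinician behaviour in family meetings, and 5.2.1 credits skills to individuals by discipline as well as to the team. A participant-level analysis is where that question would be answered. As written, a clinician who has had no CST, or only part of it, enters the post group on the same footing as one who has finished.

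The resulting estimate is an average over a mixture whose composition is not reported. If the untrained do not change, the estimate is pulled toward zero as a measure of what CST did for those who received it, and a useful training effect could be read as weak or absent. Because the study is declared unblinded (3.2 and 8.1.1), a decision on who counts as exposed is safer made before the data are examined.

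**Working it through.** **1. The plan's own figure.** The 230 meetings per period carry no baseline rate, power or alpha, so they cannot be reproduced. Against the SAP's 40% target for eliciting parental concerns (two-sided 5%, 80% power, independent meetings), a baseline of 27% needs 206 per period and 28% needs 244. A baseline in that range would fit 230, but none is stated.

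**2. Can part-trained clinicians fall in the post group?**
- The Table 1 windows overlap on days 9-200: 200 - 9 + 1 = 192 days.
- The post-CST window is 500 - 9 + 1 = 492 days, and 192/492 = 39%.
- These are study days per clinician, so 39% is an upper indication and not a share of meetings.
- The overlap may partly reflect early finishers. The interview one month after CST can occur from day 36, which implies completion near day 6 for some (36 - 30 = 6).
- That does not rescue a single initiation date: if some finish near day 6 and others near day 200, meetings in between mix completed and uncompleted training.

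**3. Are untrained clinicians in the rows?** Yes, by 3.1.5, 4.5 and 4.5.3. By head count, 300/(300 + 20) = 94% of observed clinicians are untrained. This uses the minimum of 20 trained and a 300 that is not divided by phase, so it is not the share of post-phase rows.

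**4. Does any analysis separate them?** No. Physician type, gender and years of experience are not training status. The protocol's clinician fixed effects adjust for who attended, but an untrained clinician seen in both phases still contributes to the pre/post coefficient as if exposed.

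**5. Size of the attenuation.** Let f be the trained share of post-phase rows, and assume no change in untrained clinicians. Then the pooled effect = f × the effect in trained clinicians. With 2 trained clinicians in a team of m (m assumed), f = 2/m:

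| Team size m | f |
|---|---|
| 2 | 100% |
| 3 | 67% |
| 4 | 50% |
| 5 | 40% |
| 6 | 33% |
| 8 | 25% |

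**6. What that would do to a test.** Pooled post-phase rate = baseline + f × (40% - baseline). At an assumed 20% baseline and f = 50%, this is 20% + 0.5 × 20 points = 30%. Power with 230 independent observations per period, two-sided 5%:

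| Assumed baseline | f = 100% | f = 75% | f = 50% | f = 25% |
|---|---|---|---|---|
| 10% | about 100% | about 100% | 99% | 65% |
| 20% | 99.7% | 95% | 70% | 25% |
| 30% | 61% | 40% | 21% | 8% |

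This is illustrative only. The number of participant-meeting rows is not 230, and clustering by clinician and meeting is ignored.

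**The case against.** The strongest reply is that the protocol already limits which post-phase meetings are recorded: after CST (3.1, 3.1.5, 4.5), with trained clinicians, and under 8.5 with at least two who are participating in the intervention. Section 3.1.4 requires completion of all CST parts to stay enrolled, and Table 1 labels the later window as post-CST. A short SAP need not repeat all of this. So a reader who infers that every meeting after initiation will be counted as post goes further than the documents do. What stands is that the SAP uses a different, undated cut-point. The rule in 8.5 speaks of clinicians participating, not of those who have completed CST, and 8.6.1 on selecting meetings omits it. Even when met, that rule qualifies a meeting and not each row within it.

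The second reply is that Aim 2c concerns CICU TALC, which protocol 1.2 defines as CST combined with family preparation and a written summary. Those parts can act whether or not a given clinician was trained, and an untrained colleague drawn in by a trained one is part of a team effect. This is right. A reader might infer that the comparison no longer tests anything useful, but the meeting-level analysis remains a before-after comparison of the package.

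Third, a reader might infer from the 300 that most post-phase rows are untrained. That figure counts persons across both phases, and average team size is not given, so the inference is not supported.

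Finally, making trained clinicians the only main estimate would bring its own bias. They are volunteers (3.4.2.1), and would be set against pre-phase clinicians who include non-volunteers. Untrained attendees sit in the same meetings as trained colleagues, so they are not a clean control. Both objections stand and shape the fix.

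**Conclusion.** The concern holds for the participant-meeting analysis and for the undefined cut-point. As written, the SAP pools clinicians at different stages of training, including none, under one post-intervention label that does not match the protocol's definition.

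The direction of the effect is attenuation of the CST effect in trained clinicians, provided untrained clinicians do not change. If they improve through contact with trained colleagues, the attenuation is smaller. The size cannot be derived from the documents, because team size, the trained share of rows, the baseline rate and the accrual pattern are all missing. Under the stated minimum of two, it runs from none (teams of 2) to half (teams of 4) or two thirds (teams of 6) of the effect. The meeting-level comparison of the package is not invalidated.

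**What to change.** In SAP Aim 2c:

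1. Define post-intervention meetings to match the protocol: held after CST completion, with at least two attending clinicians who have completed CST. Leave roll-in meetings out of the main comparison and add a sensitivity analysis that includes them.
2. Keep the pooled meeting-level analysis as the assessment of the package.
3. At participant-meeting level, derive each clinician's CST-completed status on the meeting date. Report post-phase results separately for trained and untrained clinicians, alongside the pooled estimate.
4. State that trained clinicians are volunteers and that untrained attendees share meetings with trained colleagues, so the untrained stratum is a descriptive reference and not a control.

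While editing, reconcile the SAP's 230 post-phase meetings with the protocol's minimum of 23 (3.1) and estimate of 28 (3.1.5).

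The cost is SAP wording and one derived variable, CST completion date against meeting date. Some roll-in recordings leave the main comparison, and the strata are smaller and less precise than the pooled group.

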3.1.5 Follow-Up Phase

Clinicians Participating in Intervention: After CST, a set of actual family meeting encounters with these trained clinicians will be audio recorded and coded, ensuring there are 23 meetings with each category of person trained. We estimate a total of 28 meetings will need to be recorded in order to obtain 23 meetings with each discipline. Clinicians participating in the intervention will complete an online survey after the actual family meeting that they are observed participating in.

This survey will measure team member perception and satisfaction with collaboration. We will administer the modified Baggs CSACD-N tool to all clinician team members who participate in an actual encounter, which will capture each discipline's experience with collaboration with other team members and satisfaction with care decisions.

Clinicians Not Participating in Intervention: Consented non-participating clinicians will have their normal, scheduled family meetings. Actual family meeting encounters with these clinicians will be audio or video recorded and coded. Clinicians not participating in the intervention will complete the same online survey as those clinicians participating in the intervention after the observed actual family meeting.

Parent-patient Dyads Participating in the Survey or Interview After Intervention: Potential subjects will be screened using the protocol inclusion and exclusion criteria. Parent-patient dyads will be recruited into the study in person, over the phone, or via e-mail. The goal for enrollment will be up to 50 parent-patient dyads, with 30 evaluable parent-

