Team function will be analyzed for simulated family meetings by comparing the change in the number of minutes that clinicians from each discipline speak in pre and post-CST meetings using linear regression and controlling for the length of the meetings.

To assess the impact of the CST program in actual family meetings, audio recordings from actual family meetings will be coded and compared to coded audio recordings from pre-intervention actual family meetings. Since there are generally at least 2 clinicians in each team encounter, we will examine the individual skill acquisition within each part of the team encounter. Within each discipline, there are several clinicians involved in multiple team meetings. We will use fixed-effects regression with a clinician identifier variable as a covariate so that we can examine the effect of CST intervention on skill acquisition, adjusting for the effects of individual clinicians.

Team function will be analyzed in the same way as in simulated meetings by comparing the change in the number of minutes that clinicians from each discipline speak in pre and post-CST meetings using linear regression and controlling for the length of the meetings.

The difference in team member perception and satisfaction with collaboration will be measured after their participation in clinical encounters both pre and post-CST by administering the modified Baggs CSACD-N tool to all clinician team members who participate in an actual encounter. This tool will capture each discipline's experience with collaboration with other team members and satisfaction with care decisions. Means and standard deviations will be calculated for the tool and t-tests will determine if there are significant differences for each discipline pre and post-CST.

Hypotheses will be tested using logistic regression modeling with significance of the two-tailed hypothesis tests set at alpha equal to 0.05.

Clinician perception of the usefulness of CST and satisfaction with the training will be identified by descriptive statistics and differences in the mean and median scores will be calculated to determine retention in perceptions of usefulness one month after the training.

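### SAP Aim 2c: misnamed and unranked speaking-time model, independence tests on clustered participant-meeting rows, and a clustered model run only after a significant univariate test

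*SAP*

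**What the plan says.** **Speaking time.** The Aim 2c analytic plan compares physician and parent word counts before and after the intervention using "generalized linear regression with binomial link function controlling for the length of the meetings". The same bullet adds that "t-tests will determine if significant differences exist for the two groups pre and post-CICU TALC". It does not rank the two analyses. It states no actual link, no denominator, no row unit and no dispersion or robust variance.

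**Skills.** Elicitation of concerns and response to emotion are compared by t, rank-sum or chi-square/Fisher tests, depending on the type of outcome. On level, "Analyses will be presented at the meeting-level as well as the participant-meeting level". Neither level is called the main one.

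**Clustered model.** "If sample size allows and there are significant univariate associations, we will utilize mixed effect regression models", which are described as "accounting for correlation of repeated measurements within participants". Correlation between people in the same meeting is not mentioned.

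**Protocol.** Section 6.3.2 begins its account of actual meetings with "Since there are generally at least 2 clinicians in each team encounter" and adds that clinicians within a discipline attend several meetings. Sections 6.3.2 and 6.4 then plan a clinician fixed-effects regression for skill acquisition, with no significance condition. The SAP neither repeats nor withdraws it.

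**Who is recorded, and how often.** Protocol 3.1.3 lists only untrained clinicians as recorded before training. Protocol 4.3 says that clinicians who will be trained are also assessed in actual encounters beforehand. The SAP states "I will audio record 230 CICU family meetings occurring before CICU TALC is initiated and 230 after initiation". Protocol 3.1.5 aims at "ensuring there are 23 meetings with each category of person trained", about 28 recordings in all.

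**The concern.** Speaking time and the two skills are the three outcomes for which Aim 2c states numerical hypotheses (60%, 40% and 30%), and the SAP tests each for significance.

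For speaking time, two analysts could follow the same sentence and fit different models. If one fits a plain binomial model that treats each word as an independent trial, the standard error is too small. That model and the t-test could then disagree, with nothing in the plan to say which counts.

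For skills, the listed tests need independent rows. Participant-meeting rows share a meeting, and often a clinician, so the tests can reject too often. The SAP model that would deal with this is reached only through the tests that ignore it.

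**Working it through.** The SAP gives no figure to reproduce here, and neither document gives word counts, spread or ICCs. All sizes below are illustrations on assumed inputs, at the protocol's two-sided alpha of 0.05.

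**1. Speaking time, if read as a plain binomial on words.** Assume a parent share p = 0.20, w words per meeting and a between-meeting SD of the share s. The variance is understated by the factor φ = 1 + (w − 1)s²/[p(1 − p)], and true alpha = 2[1 − Φ(1.96/√φ)].
- w = 500, s = 0.02: φ = 1 + 499 × 0.0004/0.16 = 2.25, alpha 0.19.
- w = 8,000, s = 0.10: φ = 1 + 7,999 × 0.01/0.16 = 501, alpha 0.93.

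A spread this wide means that the size is unknown. In simulation at 23 and 230 meetings per period, a quasi-binomial model rejected 5.0–7.0% of the time, a robust fractional logit 3.6–5.9%, and a t-test on one share per meeting 3.5–5.9%.

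**2. Row-level skill tests.** Take 23 meetings per period and m = 4 clinicians per meeting (assumed; the protocol says at least 2). Let ρc and ρm be the clinician and meeting ICCs. If a clinician attends each meeting with probability q, the clinician part of the variance inflation in a period is 22qρc, because (23 − 1)q is the expected number of further rows from the same person. The meeting part is (m − 1)ρm. Clinicians seen in both periods partly cancel out of the difference.

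The averaged inflation is V = 1 + 3ρm + Cρc, where C is the mean of 22q over the two periods less the expected cross-period overlap:
- *Same 20 clinicians in both periods:* q = 4/20, so C = 4.4 − 23 × 0.2 = −0.2, about zero. Only the meeting part remains.
- *Mixed post-training team:* 4 of 150 before; 2 of 20 trained plus 2 of the same 150 after. Before: 22 × 4/150 = 0.587. After: the average of 22 × 0.1 = 2.2 and 22 × 2/150 = 0.293, which is 1.247. Overlap: 23 × 2/150 = 0.307. C = (0.587 + 1.247)/2 − 0.307 = 0.61.
- *All post-training attendees trained:* 4 of 150 before, 4 of 20 after. C = (0.587 + 4.4)/2 = 2.49.

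The 20 and the minimum of two trained clinicians per meeting come from protocol 3.1.1 and 8.5. The 150 is an assumption, half of the roughly 300 untrained clinicians in protocol 3.3.2.

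At ρm = 0.3 and ρc = 0.2, taking C as zero for the same clinicians:

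| Scenario | V | alpha from V |
|---|---|---|
| Same clinicians | 1.90 | 0.155 |
| Mixed team | 1 + 0.9 + 0.12 = 2.02 | 0.168 |
| All trained | 1 + 0.9 + 0.50 = 2.40 | 0.206 |

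Simulation over ρc 0.1–0.2 and ρm 0–0.3 agrees: about 5–16% for the first two scenarios (the approximation puts the top of the mixed case at 17%), and up to 0.216 for the third. With the same clinicians and ρm = 0 it is about 5%. With two clinicians per meeting the ranges fall to 5–9% (same) and 6–12% (all trained).

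**3. Meeting-level tests.** A test on meeting means already carries the meeting part, so the remaining inflation is V/(1 + 3ρm). At ρc = 0.2 and ρm = 0.3 this is 2.02/1.90 = 1.06 (alpha 0.057) for the mixed team and 2.40/1.90 = 1.26 (alpha 0.081) for all trained. At ρm = 0 it is 1.12 (0.064) and 1.50 (0.109). Simulated values are about 5% with the same clinicians, about 6–7% with a mixed team and about 8–10% with all trained. Both departures are smaller at ρc = 0.1.

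**4. The gate.** Same 20 clinicians, two per meeting, ρc = 0.2, ρm = 0.1. At 23 meetings and a true standardised effect of 0.3, power of the adjusted analysis falls from 0.305 to 0.260, and adjusted estimates that pass the gate average 1.74 times the truth. At an effect of 0.5 the ratio is 1.22. At 230 meetings and an effect of 0.3, power is 0.997 ungated and 0.991 gated, and the ratio is 1.00.

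**5. Is a clinician effect alone enough?** In simulated REML fits at 23 meetings (continuous score, ρc = 0.2, ρm 0.1 or 0.3), a clinician effect alone rejected 5–18% of the time. Clinician plus meeting effects with Satterthwaite degrees of freedom rejected 3.5–6.2%.

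**6. Can the protocol's fixed-effects model be fitted?** If no clinician is recorded in both periods, the period indicator is the sum of the indicators of the post-period clinicians. In a worked example the design matrix had 35 columns and rank 34, so the period effect could not be estimated. With the same clinicians in both periods it had 21 columns and rank 21.

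**The case against.** These are secondary analyses in a pilot with a qualitative primary endpoint (protocol 6.1). The SAP offers its mixed model as exploration and guards it with a sample-size condition. It also plans meeting-level results, and protocol 5.2.1 credits skills to the team as a whole, so the meeting is a legitimate unit. All of this stands and lowers the stakes.

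Three stronger readings are tempting, and the documents do not support them.
- A reader might infer that a skill failing the univariate test never receives a clinician-adjusted estimate. That follows from the SAP alone, but protocol 6.3.2 and 6.4 plan an ungated clinician fixed-effects model that nothing withdraws. The fault is two unreconciled plans.
- A reader might infer that the speaking-time test has a grossly inflated error rate. That needs a binomial family, words as independent trials and dispersion fixed at 1, none of which the SAP states. A count model with its own dispersion is also a possible reading, and the problem then disappears.
- A reader might infer that the gate raises type I error. It does not: requiring a second significant result cannot increase unconditional rejection by the mixed model. At the SAP's 230 meetings it costs almost nothing.

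Steeper clustering figures can be produced by supposing two separate pools of 20 clinicians, but no section describes such a design. Protocol 4.5 and 8.5 describe mixed teams after training, for which the meeting-level test is close to nominal.

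**Conclusion.** The point holds and should be fixed before analysis, at moderate weight. The defects lie in the row-level tests, the gate and the speaking-time sentence; the meeting-level tests are largely sound.

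- **Speaking time:** the model is misnamed, has no unit or dispersion and is not ranked against the t-tests. Any understatement of the standard error depends on how the sentence is read, and its size cannot be known from the documents.
- **Skills:** at 23 meetings per period and four clinicians per meeting, row-level null rejection is about 5–16% with the same clinicians or a mixed team, and up to about 22% if all post-training attendees are trained. This rests on the assumed ICCs and pool sizes. The meeting part of the inflation does not shrink as meetings are added.
- **Gate:** at about 23 meetings it selects adjusted estimates that are too large. At 230 it matters little.
- **Model content:** the SAP's mixed model names no meeting effect, and whether the protocol's alternative can be estimated depends on who is recorded before training, on which protocol 3.1.3 and 4.3 differ.

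**What to change.** 1. **Speaking time.** Analyse one parent speaking share per meeting with a quasi-binomial or robust-variance fractional logit model, or with a meeting-level t-test. State family, link and unit, and name one of these as the main analysis.
2. **Skills.** Make a mixed model with clinician and meeting random effects, with small-sample degrees of freedom, the main participant-level analysis, and run it whatever the univariate result. Keep row-level tests descriptive and show meeting-level results alongside.
3. **Fallback.** Say what is reported if the model does not converge for a rare binary skill, for example the meeting-level test.
4. **Reconcile** the SAP's Aim 2c plan with protocol 6.3.2 and 6.4, and protocol 3.1.3 with 4.3. Clinician fixed effects can estimate the period effect only if some clinicians are recorded in both periods. If those are only untrained clinicians, the estimate is not the effect of training on the people trained.

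The cost is a few SAP sentences and no new data. Intervals will be wider, and non-convergence is a real possibility at 23 meetings. The two-way model's error rate was checked only for a continuous score.
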